9.1. DERIVATIONS

- Time to discontinuation of the double-blind treatment in days

For the purpose of this analysis, a subject's last dose date will be derived as follows:

- If a subject's observed last dose date is before or on the date of Study Day 364, the derived last dose date will be set to the observed last dose date.
- If a subject's observed last dose date is after the date of Study Day 364, the derived last dose date will be set to the date of Study Day 364.

Time to discontinuation (days) = Derived last dose date – First dose date + 1.

Subjects who complete the double-blind treatment will be censored on the derived last dose date.

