5.3. Other Efficacy Objectives

- To evaluate the long-term effectiveness of SEP-363856 and quetiapine XR using the
 - Positive and Negative Syndrome Scale (PANSS)
 - Clinical Global Impression-Severity (CGI-S) scale
 - Brief Negative Symptom Scale (BNSS)
 - Montgomery-Asberg Depression Rating Scale (MADRS)
- To evaluate the maintenance efficacy of SEP-363856 and quetiapine XR (including time to relapse, rate of relapse and frequency of hospitalization due to relapse)
- To evaluate adherence to study treatment based on time to all cause discontinuation
- To evaluate the effects of SEP-363856 and quetiapine XR on daytime sleepiness as measured by the Epworth Sleepiness Scale (ESS)
- To assess the effects of SEP-363856 and quetiapine XR on cognition as measured by the Brief Assessment of Cognition in Schizophrenia (BACS)

- To explore the effects of SEP-363856 and quetiapine XR on functional capacity as measured by the University of California San Diego (UCSD) Performance-Based Skills Assessment – Brief Version (UPSA-B).
- To evaluate the effects of SEP-363856 and quetiapine XR on function as measured by the Specific Level of Functioning Scale (SLOF)
- To evaluate the effects of SEP-363856 and quetiapine XR on health-related quality of life as measured by the EuroQol-5D-5L (EQ-5D-5L)
- To evaluate medication satisfaction as measured by the Medication Satisfaction Questionnaire (MSQ)
- To explore the impact of SEP-363856 on nicotine use

5.4.

CCI

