15.3. Data Analysis

15.3.1. Subject Disposition

Subject disposition will be summarized by the actual treatment group (if applicable) and overall for all subjects. The number and percent of subjects, who are screened, screen-failed, randomized, received study drug, and completed or discontinued early from the double-blind treatment period (including reasons for discontinuation) will be presented.

As exploratory analysis, the time-to-discontinuation (any reason) by treatment will be summarized descriptively and will also be tested with log-rank statistic and presented by a Kaplan-Meier plot.

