7.2. MULTICENTER STUDIES

This study will be conducted by multiple Investigators at multiple centers in the US and non-US countries, including Russia, Romania, and Ukraine. Randomization is stratified by country.

When specified, statistical analysis will be adjusted for country.

Document: CCI

Author: PPD

Version Number: 0.6

Version Date: 30JAN2023

Template No.: CS_TP_BS016 Revision 6

Reference: CS_WI_BS005

Effective Date: 02Dec2019

A term for treatment-by-country interaction at Week 52/Visit 17 will be explored as part of the subgroup analysis (see [Section 16.1.1.4](#)). A significant interaction effect is defined as having a nominal p- value ≤ 0.10 . Additionally, graphical methods (i.e. Forest plots) will be used to present the analysis results separately for each country and to assess whether the interaction, if there is one, is quantitative (i.e. the treatment effect is consistent in direction but not in size) or qualitative (i.e. the treatment is beneficial for some but not for other countries).

Center pooling will not be implemented in the analyses for this study.

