9. DISPOSITION AND WITHDRAWALS

Unless otherwise specified, the disposition summary tables will include the following columns:

SEP-363856 50 to 100 mg/day, Quetiapine XR 400 to 800 mg/day, and Total.

All subjects who provide informed consent will be accounted for in this study.

Subject disposition will be presented by the actual treatment group (where applicable). The number and percentage of subjects who were screened, screen failed, randomized, received study drug, randomized but did not receive study drug, and completed or discontinued from the double-blind treatment period (including reasons for discontinuation) will be presented. Disposition will be presented separately for each country as well.

With respect to the above, the following definitions apply:

- Screened Subjects: Any subject who signed the study specific informed consent.
- Screen Failures: Any subject who signed the study specific informed consent but either failed to meet study requirements during screening or met study requirements at screening and was not randomized.
- Randomized Subjects: Any subject who was randomized into treatment period of the study and was assigned a randomization number.

Subjects who were screened more than once will be counted only once in the disposition summary based on the outcome of the last screening. If a subject failed multiple screenings, they will only be counted once as a screen failure. If a subject is randomized after multiple screenings, they will only be counted once as a randomized subject.

Discontinuation by visit will be summarized for the SAF population by the actual treatment group.

Time to discontinuation of the double-blind treatment since first dose of study drug will be plotted using Kaplan-Meier curves for the SAF population by the actual treatment group. The log rank testing method will be used to test for differences among the treatment groups for time to discontinuation.

Document: CCI

Author: PPD

Version Number: 0.6

Version Date: 30JAN2023

Template No.: CS_TP_BS016 Revision 6

Reference: CS_WI_BS005

Effective Date: 02Dec2019

The number and percentage of subjects will also be summarized by Region, Country, and Site, by the actual treatment group for the SAF population.

Lastly, the number and percentage of randomized subjects included in and excluded from each analysis population will be summarized by the actual treatment group, along with the reason for exclusion.

COVID-19 related analysis updates:

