The number of subjects who failed screening due to COVID-19 related reasons and who discontinued early due to COVID-19 related reasons will be summarized in the disposition table.

Subjects affected by COVID-19 related study disruptions will be provided in data listings. These subjects will be identified by:

- Subjects who failed screening due to COVID-19 related reasons.
- Subjects who were randomized but discontinued from the treatment period due to COVID-19 related reasons.
- Subjects who experienced a pre-treatment event / adverse event related to COVID-19.
- Subjects who had any protocol deviations related to COVID-19.
- Subjects who had any investigator comments related to COVID-19.

A subject may be identified in one or more categories listed above.

Russia-Ukraine geopolitical conflict related analysis:

The number of subjects who discontinued early due to geopolitical conflict related reasons will be summarized in the disposition table.

Subjects affected by geopolitical conflict related study disruptions will be provided in data listings. These subjects will be identified as:

- *Subjects who discontinued from the treatment period due to geopolitical conflict.*
- *Subjects who experienced an adverse event related to geopolitical conflict.*
- *Subjects who had any protocol deviations related to geopolitical conflict.*
- *Subjects who had any investigator comments related to geopolitical conflict.*

A subject may be identified in one or more categories listed above.

Document: CCI

Author: PPD

Version Number: 0.6

Version Date: 30JAN2023

Template No.: CS_TP_BS016 Revision 6

Reference: CS_WI_BS005

Effective Date: 02Dec2019

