16.1.1.2. Sensitivity Analyses of PANSS Total Score

Patterns of the observed data in the exploratory endpoint will be examined through graphical tools based on the reason and the timing of study treatment withdrawal.

Mean change from Baseline in PANSS total score at each time point will be plotted by the reason of early discontinuation (adverse event [separately by COVID-19 relatedness], lack of efficacy, lost to follow-up, withdrawal by subject, non-compliance with study drug, protocol deviation, death [separately by COVID-19 relatedness], pregnancy, other [separately by COVID-19 relatedness]) and for completers, separately for each treatment group. Similar reasons may be combined, depending on the number of subjects who

Document: CCI

Author: PPD

Version Number: 0.6

Version Date: 30JAN2023

Template No.: CS_TP_BS016 Revision 6

Reference: CS_WI_BS005

Effective Date: 02Dec2019

discontinued under each reason. Reason pooling will be determined at the Blinded Data Review meeting prior to database lock and treatment unblinding.

Mean change from baseline in PANSS total score at each time point will also be plotted by the timing of early discontinuation (Week 1 terminators, Week 4 terminators, Week 8 terminators, Week 16 terminators, Week 24 terminators, Week 32 terminators, Week 40 terminators, Week 48 terminators, Week 52 terminators) and for completers, separately for each treatment group.

- Week 1 terminators: subjects who discontinue after Visit 2 but before or on Visit 3;
- Week 4 terminators: subjects who discontinue after Visit 3 but before or on Visit 5;
- Week 8 terminators: subjects who discontinue after Visit 5 but before or on Visit 6;
- Week 16 terminators: subjects who discontinue after Visit 6 but before or on Visit 8;
- Week 24 terminators: subjects who discontinue after Visit 8 but before or on Visit 10;
- Week 32 terminators: subjects who discontinue after Visit 10 but before or on Visit 12;
- Week 40 terminators: subjects who discontinue after Visit 12 but before or on Visit 14;
- Week 48 terminators: subjects who discontinue after Visit 14 but before or on Visit 16;
- Week 52 terminators: subjects who discontinue after Visit 16 but before Visit 17 (the EOT visit).

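### Time to all-cause discontinuation serves the adherence objective, but no planned analysis sets aside stops forced by the Russia-Ukraine conflict or COVID-19 logistics

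*SAP*

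**What the plan says.** The objective is the same in Protocol 5.3 and SAP 2.1.3: "To evaluate adherence to study treatment based on time to all cause discontinuation". Protocol 15.3.1 plans the analysis as exploratory: "the time-to-discontinuation (any reason) by treatment will be summarized descriptively", with a log-rank test and a Kaplan-Meier plot. SAP 9 repeats this for the safety population by actual treatment: "The log rank testing method will be used to test for differences among the treatment groups for time to discontinuation". It mentions no stratification of the test.

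SAP 9.1 sets the time variable as first dose to derived last dose, capped at Study Day 364, and gives one censoring rule: "Subjects who complete the double-blind treatment will be censored on the derived last dose date". Every other subject is therefore an event at the derived last dose date, whatever the reason for stopping.

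The SAP recognises both external disruptions. On the conflict, SAP 9 says: "The number of subjects who discontinued early due to geopolitical conflict related reasons will be summarized in the disposition table". For COVID-19 it gives the number of those "who discontinued early due to COVID-19 related reasons will be summarized in the disposition table". Affected subjects are also listed. SAP 5 states that neither disruption changed any population definition. Besides the US, SAP 7.2 names "non-US countries, including Russia, Romania, and Ukraine", so Russia and Ukraine are two of the four countries listed in SAP 7.1. Randomization is stratified by country.

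**The concern.** A subject whose site could no longer operate, or who was displaced, enters the curve exactly as one who stopped for intolerance or lack of effect. For a statement about how many subjects left for any reason, that is what is wanted. For a statement about adherence it mixes two things. A stop forced from outside says little about whether the subject would have stayed on the drug.

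The SAP identifies these subjects but does not carry the identification into the time-to-event analysis. Two readings could suffer. One-year retention, read as adherence, would look worse than it was in both arms. The comparison between arms could also be distorted, in a direction that depends on how external stops fall across the arms.

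**Working it through.** **Plan's own figure.** 300 × 2/3 = 200 subjects on SEP-363856; 80 expected one-year completers / 200 = 40% (Protocol 15.1, SAP 3.4). No dropout rate is given, so the 80 cannot be derived. As a plausibility check only, Protocol 4.1 cites 70% to 80% discontinuing before 18 months. With a constant hazard, one-year retention is 0.30^(12/18) = 45% down to 0.20^(12/18) = 34%, or about 90 to 68 of 200. The 40% is a reasonable anchor.

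**Assumed inputs (not in the documents).** Net external loss by one year, e: 5%, 10% or 20%, the same in both arms. Here e is the proportion who would be lost to external causes if nothing else stopped them. Hazard ratio without external stops: 0.70. Comparator retention without external stops: 40%.

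**Retention.** If external stops are independent of other stops, all-cause retention = retention without external stops × (1 − e). Taking the 40% as the all-cause figure shown:
- e = 5%: 0.40/0.95 = 42.1%
- e = 10%: 0.40/0.90 = 44.4%
- e = 20%: 0.40/0.80 = 50.0%

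This step needs independence but not constant hazards.

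**Hazard ratio.** With constant hazards, λ0 = −ln 0.40 = 0.916 for quetiapine XR, λ1 = 0.70 × 0.916 = 0.641 for SEP-363856, and μ = −ln(1 − e) for external stops. The all-cause hazard ratio is (λ1 + μ)/(λ0 + μ). For e = 10%, μ = 0.105 and the ratio is 0.747/1.022 = 0.731.

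**Power.** With d expected events, 2:1 allocation and two-sided 5%: Φ(√(d × 2/3 × 1/3) × |ln HR| − 1.96).

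| e | External events expected (of 300) | HR, counted | Events, counted / censored | Power, counted / censored |
|---|---|---|---|---|
| 5% | 11 | 0.716 | 162 / 151 | 51.8% / 54.3% |
| 10% | 21 | 0.731 | 169 / 148 | 48.5% / 53.3% |
| 20% | 43 | 0.759 | 184 / 141 | 42.2% / 51.3% |

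The extra events from counting external stops do not make up for the hazard ratio moving toward 1. The same direction appears for underlying hazard ratios of 0.60 to 0.80 with comparator retention of 30% to 50%. At e = 20%, counting costs about 4 to 14 points of power against censoring.

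**Where the dilution fails.** With no true difference, (λ + μ)/(λ + μ) = 1, so only retention is lowered. With unequal external loss the direction is open. Starting from 0.70, loss of 10% on SEP-363856 and 5% on quetiapine XR gives (0.641 + 0.105)/(0.916 + 0.051) = 0.77. The reverse gives (0.641 + 0.051)/(0.916 + 0.105) = 0.68.

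**The case against.** The strongest answer is that the rule is correct. Protocol 6.3 and SAP 2.2.3 name the endpoint as all-cause, Protocol 15.3.1 says any reason, and censoring only completers is what that means. A reader might infer that SAP 9.1 contains a censoring error, or that all-cause retention is understated. Neither follows: retention is low only relative to a different quantity, which the plan does not define.

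A reader might also infer that the arm comparison is diluted as a matter of course. That needs a true difference and similar external rates by arm. Stratification by country makes balance likely for the conflict but does not guarantee it.

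Other parts of the answer stand too. The analysis is exploratory, its p-values are nominal (SAP 7.4), and no power is claimed for it. Drug-taking is assessed separately by capsule count (Protocol 10.2, SAP 15). The disposition table, by arm and by country, lets a reader see how many external stops there were.

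Censoring has its own weaknesses. It assumes independent censoring and relies on attributed reasons, and the discontinuation reasons in Protocol 13.1 include no conflict category. COVID-19 relatedness is broader than logistics: the PANSS plots in SAP 16.1.1.2 split adverse event and death by it, as well as "other [separately by COVID-19 relatedness". Censoring all of these would remove clinical events. So it would be too strong to say that external stops carry no information, or that a censored analysis should replace the named endpoint for the adherence conclusion.

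What the objection does not supply is an analysis that sets these stops aside. Counts do not show when the stops happened or what they do to the curves. Nor is the technique foreign to this SAP: for time to relapse, SAP 16.2.12 already censors subjects who discontinue without relapsing.

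**Conclusion.** The point holds as a gap in support for the adherence objective, not as an error in the all-cause endpoint. Read as adherence, 40% shown retention would correspond to about 42% to 50%. A hazard ratio of 0.70 would appear as about 0.72 to 0.76, given a true difference and equal external loss.

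These sizes rest on an assumed 5% to 20% net external loss; the documents give neither the number of such stops nor the country shares. The hazard ratios also assume constant hazards over study time, which only approximates a disruption that strikes at a calendar date. At the low end the effect is minor for an exploratory test without stated power. The primary safety endpoint is unaffected. This is a cheap improvement to what the trial can say about adherence.

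**What to change.** Keep time to all-cause discontinuation, with its present censoring rule, as the named endpoint. Add to SAP 9 and 9.1 one sensitivity Kaplan-Meier and log-rank analysis in which discontinuations due to the conflict or to COVID-19 logistics are censored at the derived last dose date. State that COVID-19 illness adverse events and COVID-19 deaths remain events. Flag the affected subjects in blinded review before unblinding, building on the identification SAP 9 already requires. Report the result beside the all-cause result when interpreting adherence, and note its reliance on attributed reasons and independent censoring.

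The cost is one extra table and one extra figure, plus blinded review time to separate COVID-19 logistics from illness.

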10. IMPORTANT PROTOCOL DEVIATIONS

Important protocol deviations (IPDs) will be identified and documented based on blinded reviews of data listings and the protocol deviations log.

Unless otherwise specified, the IPD summary tables will include the following columns: SEP-363856 50 to 100 mg/day, Quetiapine XR 400 to 800 mg/day, and Total.

The IPD categories may include, but may not be limited to:

- Did not satisfy inclusion and/or exclusion criteria
- Received prohibited medication
- Overall double-blind compliance rate <75% or >125%

The IPDs will be identified for all randomized subjects and presented in a data listing. The number and percentage of subjects within each IPD category will be summarized by the actual treatment group for the SAF population.

A dedicated listing will present protocol deviations related to COVID-19 in randomized subjects. A separate dedicated listing will present protocol deviations related to the Russia-Ukraine geopolitical conflict in all enrolled subjects.

Two sets of clinical trial management system (CTMS) deviation categories are used in the study: former

Document: CCI

Author: PPD

Version Number: 0.6

Version Date: 30JAN2023

Template No.: CS_TP_BS016 Revision 6

Reference: CS_WI_BS005

Effective Date: 02Dec2019

categories used for deviations reported up to 15MAY2022 and new categories for deviations reported as of 16MAY2022. These categories will be presented as is in the listings.

11. DEMOGRAPHIC AND OTHER BASELINE CHARACTERISTICS

Unless otherwise specified, the demographic and Baseline characteristics summary tables will include the following columns: SEP-363856 50 to 100 mg/day, Quetiapine XR 400 to 800 mg/day, and Total.

Demographic data and other Baseline characteristics will be presented for the SAF population, EFF population, and PP population. For the EFF and PP populations, the data will be presented by the randomized treatment group. For the SAF population, the data will be presented by the actual treatment group. Basic demographic data (age, sex, race, ethnicity, country, and region) will also be summarized for all screened subjects by randomization status (i.e. randomized vs. not randomized).

No statistical testing will be carried out for demographic or other Baseline characteristics.

The following demographic and other Baseline characteristics will be reported for this study:

- Age (years) - calculated relative to date of informed consent as a continuous variable
- Age (years) categories:
 - <18 years
 - ≥ 18 to ≤ 40 years
 - >40 to ≤ 65 years
 - >65 years
- Age (years) categories for ClinicalTrials.gov (CTR.GOV):
 - ≤ 18 years
 - >18 to <65 years
 - ≥ 65 years
- Age (years) categories for European Union Drug Regulating Authorities Clinical Trials Database

Document: CCI

Author: PPD

Version Number: 0.6

Version Date: 30JAN2023

Template No.: CS_TP_BS016 Revision 6

Reference: CS_WI_BS005

Effective Date: 02Dec2019

(EudraCT):

- <12 years
- ≥12 to <18 years
- ≥18 to <65 years
- ≥65 years
- Sex
 - Female
 - Male
- Race
 - American Indian or Alaska Native
 - Asian
 - Black or African American
 - Native Hawaiian or Other Pacific Islander
 - White
 - Multiracial
 - Other
- Ethnicity
 - Hispanic or Latino
 - Not Hispanic or Latino
- Country
 - United States
 - Russia

Document: CCI

Author: PPD

Version Number: 0.6

Version Date: 30JAN2023

Template No.: CS_TP_BS016 Revision 6

Reference: CS_WI_BS005

Effective Date: 02Dec2019

- Romania
- Ukraine
- Geographic Region
 - US
 - Non-US
- Baseline Height (cm), as a continuous variable
- Baseline Weight (kg), as a continuous variable
- Baseline BMI (kg/m²), as a continuous variable
- Baseline BMI (kg/m²) category
 - Underweight: <18.5 kg/m²
 - Normal: ≥18.5 to <25.0 kg/m²
 - Overweight: ≥25.0 to <30.0 kg/m²
 - Obese: ≥30.0 kg/m²
- Baseline Waist Circumference (cm), as a continuous variable
- Baseline PANSS Total Score, as a continuous variable
- Baseline PANSS Total Score categories:
 - <Overall median Baseline value
 - ≥Overall median Baseline value
- Baseline PANSS Subscale Scores, as continuous variables
- Baseline PANSS Subscale Score categories:
 - <Overall median Baseline value
 - ≥Overall median Baseline value

Document: CCI

Author: PPD

Version Number: 0.6

Version Date: 30JAN2023

Template No.: CS_TP_BS016 Revision 6

Reference: CS_WI_BS005

Effective Date: 02Dec2019

- Baseline PANSS Positive vs Negative Subscale Score categories:
 - Positive Subscale Score < Negative Subscale Score
 - Positive Subscale Score \geq Negative Subscale Score
- Patient type based on Baseline UPSM factor scores
 - Type 1: Prominently Disorganized
 - Type 2: Prominently Negative
 - Type 3: Prominently Hostile
 - Type 4: Prominently Positive
 - Type 5: Prominently Affective
- Baseline CGI-S Score, as a continuous variable
- Baseline CGI-S Score categories:
 - <4
 - =4
 - >4

The following psychiatric history data will be summarized for the SAF population, EFF population, and PP population in separate tables. For the EFF and PP populations, the data will be presented by the randomized treatment group. For the SAF population, the data will be presented by the actual treatment group.

- Time since initial onset of schizophrenia (years) – calculated relative to date of informed consent.
- Time since initial onset of schizophrenia (years) categories:
 - <5 years
 - \geq 5 to <10 years
 - \geq 10 to <20 years

Document: CCI

Author: PPD

Version Number: 0.6

Version Date: 30JAN2023

Template No.: CS_TP_BS016 Revision 6

Reference: CS_WI_BS005

Effective Date: 02Dec2019

- ≥ 20 years
- Age at initial onset of schizophrenia (years)
- Time since schizophrenia diagnosis (years) – calculated relative to date of informed consent
- Time since last acute exacerbation of schizophrenia (days) – calculated relative to date of informed consent
- DSM-5 schizophrenia subtype diagnosis
 - 295.90 Schizophrenia
 - 293.89 Schizophrenia with Catatonia
- Number of prior hospitalizations for treatment of schizophrenia
 - 0
 - 1
 - 2
 - 3
 - 4 or more
- Time since first hospitalization for treatment of schizophrenia (years) – calculated relative to date of informed consent
- Age at first hospitalization for treatment of schizophrenia (years)
- Time since first anti-psychotic drug therapy of at least 2 weeks duration intended for treatment of schizophrenia (years) – calculated relative to date of informed consent
- Age at first anti-psychotic drug therapy of at least 2 weeks duration intended for treatment of schizophrenia (years)
- Any other psychiatric disorders
 - Yes

Document: CCI

Author: PPD

Version Number: 0.6

Version Date: 30JAN2023

Template No.: CS_TP_BS016 Revision 6

Reference: CS_WI_BS005

Effective Date: 02Dec2019

- No

Diagnosis and DSM-5 code for any current psychiatric disorders will be summarized in a separate table. These other current psychiatric disorders will be coded using Medical Dictionary for Regulatory Activities (MedDRA) central coding dictionary, Version 22.0, and presented by System Organ Class (SOC), and Preferred Term (PT).

